## **10. STATISTICAL ANALYSIS**

### **10.1. Primary study parameter(s)**

Different cardiopulmonary parameters will be presented by means and standard deviations and will be compared between the groups using an independent t-test, with Bonferroni correction if applicable.

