#### *Patient population*

As many of our EC patients are older and have cardiopulmonary problems as a result of their age, co-morbidities or lifestyle habits, we would like to compare a cohort of patients treated for EC who did or did not undergo (chemo)radiotherapy.

A cohort of these patients is available, as neo-CRT has become standard treatment since 2012 after the publication of the so-called CROSS trial, demonstrating an important survival benefit in the group that received neo-CRT followed by surgery compared to patients treated with surgery alone. During this time period and the time period shortly before and after, patients were treated either with or without neo-CRT. In this time period we did not select patients on cardiopulmonary co-morbidities or age, so we expect comparable groups. Part of these patients were already retrospectively analyzed and compared on short term (within 90 days) morbidity and mortality after resection [23]. These data were published in 2013. We demonstrated an increased incidence of pneumonia and rhythm disorders in patients treated with neo-CRT, but no difference was noted in neither hospital and intensive care unit stay nor in mortality or overall morbidity between these two groups. As these patients were treated in the time period 2000-2012 and thus will have a 5-15 years follow up there is a sufficiently large patient cohort available to prospectively analyze clinical and subclinical cardiac changes and/or toxicities.

*Which tests would be interesting at longer follow up or study parameters*

As mentioned in the introduction, the main focus of this study is (subclinical) cardiopulmonary (dys)functioning. The most important late (subclinical) toxicities we expect to find at longer follow up are: diastolic dysfunction, coronary artery disease, cardiac wall motion disorders, heart failure, pulmonary hypertension, pericardial effusion and/or constriction, cardiac arrhythmia and valve disorders. A number of these endpoints will eventually result in heart failure.

- Anamnesis and physical examinations will be performed in these patients
- In case a pulmonologist or cardiologist has been consulted, additional information will be collected from hospital records of these specialists.
- Radiotherapy treatment parameters will be collected from our database in case the patient was treated with radiotherapy.
- 6 minute walking test
- Echocardiogram
- CT scan
- Cardiac MRI scan
- ECG

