### **4. OTHER STUDY PARAMETERS**

For the purpose of this study, the following parameters will be assessed in all patients:

- Cardiac risk factors
  - Smoking status
  - Age
  - Detailed cardiac history including medical letters from cardiologists when available
  - Detailed pulmonary history including medical letters from pulmonologists when available
  - Alcohol consumption
  - Family history on cardiac events
  - Hypertension
  - D.M.
  - Use of medication
- Combination with chemotherapy
- Postoperative complications and interventions
- Sex
- Daily activities and/or sport

- Original clinical tumor stage (TNM)
- Original tumour length at endoscopy
- Original pathologic tumor stage (TNM)
- Volume (cc) of the irradiated planning target volume
- For irradiated patients; radiotherapy treatment parameters and dose distributions
  - Dose Volume Histogram of the heart
  - Dose Volume Histogram of different cardiac subvolumes
  - Dose Volume Histogram of the lungs

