## **5. STUDY DESIGN**

This is a cross sectional pilot study with patients who were or were not treated with neo-CRT.

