## 7. SAMPLE SIZE CALCULATION

As this is a pilot study to determine (sub-clinical) cardiopulmonary toxicity, a total of 40 patients, 20 in each group, will be included in this study.

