## 8. METHODS

### 8.1. Randomisation, blinding and treatment allocation

Not applicable

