### **10.2. Other study parameters**

Risk factors for cardiac and pulmonary complaints will be presented in frequency tables and tested for statistical significant differences between both groups using an independent t-test

Location of focal wall abnormalities and arteriosclerosis and its relation to high dose regions will be presented in a table.

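### The only stated group comparison is an unadjusted t-test between non-randomised groups, so any imbalance in age, sex or smoking would pass into the estimated difference

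*Protocol*

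**What the plan says.** - **Design.** Section 5: "This is a cross sectional pilot study with patients who were or were not treated with neo-CRT". Section 8.1, headed "Randomisation, blinding and treatment allocation", is marked as not applicable. Section 7: "a total of 40 patients, 20 in each group, will be included in this study".
- **Group comparison.** Section 10.1: the parameters are summarised by mean and SD and "will be compared between the groups using an independent t-test". A Bonferroni correction, where applicable, is the only refinement.
- **Risk factors.** Section 10.2: these are tabulated and "tested for statistical significant differences between both groups using an independent t-test". It does not say what follows if a difference is found.
- **Why there is a control group.** Section 1, Patient population, says that many of these patients "have cardiopulmonary problems as a result of their age, co-morbidities or lifestyle habits". It then expects the groups to be comparable, because age and cardiopulmonary co-morbidity played no part in selection in that period.
- **Data collected.** Section 4 lists smoking, age, hypertension and diabetes under "Cardiac risk factors". Sex is listed separately.
- **Confounding.** The only explicit remark is in section 6.1. It concerns length of follow-up, which it sets aside.

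**The concern.** The protocol names age, co-morbidity and lifestyle as causes of the outcomes under study and collects these factors in everyone. It then leaves them out of the outcome comparison. A two-sample t-test attributes the whole difference in means to the treatment group, so a difference in age, sex or smoking is counted as an effect of neo-CRT. The test in section 10.2 is no safeguard: at this size a non-significant result says little about balance, and a significant one has no stated consequence.

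Two things are at stake. Estimating the group difference is part of the main objective (section 2). The results are also meant to identify the most promising tests for a later cohort (section 11.4). A test that mainly tracks age or smoking could look like a marker of radiation damage, and a useful one could be masked.

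**Working it through.** **Inputs.** From the protocol: 20 per group, independent t-test. It states no alpha, sidedness, power, effect size or SD, so the figure of 40 cannot be reproduced. Assumed here: two-sided 0.05, effects in SD units, and the imbalances and covariate effects shown below.

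**1. Power of the section 10.2 check.** With n = 20 per group the test has 38 df, critical value 2.0244 and noncentrality d × √(n/2) = 3.162 d.

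- Age gap of 5 years, SD 10: d = 0.5, noncentrality 1.58, power 34%.
- Age gap of 5 years, SD 8: d = 0.625, noncentrality 1.98, power 49%.
- Power of 80% needs d = 0.91.
- Binary factor, 50% vs 70%: power 25%. 50% vs 80%: 51%.
- Smoking, 40% vs 65%: 23% (Fisher) or 33% (t-test).

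**2. Imbalance by chance alone.** Summing the two binomial distributions over count differences of 4 or more out of 20 gives a gap of at least 20 points in 27% of samples at prevalence 50%, and in 23% at 30% or 70%.

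**3. Bias passed on when there is no true effect.** Bias = imbalance × covariate effect. Type I error is the rejection rate of the unadjusted t-test at that bias.

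| Assumed imbalance and effect | Bias (SD) | Type I error |
|---|---|---|
| Age 0.3 SD, correlation 0.3 | 0.3 × 0.3 = 0.09 | 6% |
| Age 0.5 SD, correlation 0.5 | 0.5 × 0.5 = 0.25 | 12% |
| Age 0.7 SD, correlation 0.6 | 0.7 × 0.6 = 0.42 | 25% |
| Binary, 20 points, effect 0.5 SD | 0.2 × 0.5 = 0.10 | 6% |
| Binary, 30 points, effect 1.0 SD | 0.3 × 1.0 = 0.30 | 13% |
| Age 0.2 SD and smoking 10 points, both effects 0.3 | 0.06 + 0.03 = 0.09 | 5.7% |
| Age 0.25 SD (slope 0.4) and smoking 12.5 points (0.5 SD) | 0.10 + 0.0625 = 0.16 | 8% |
| Age 0.5 SD (slope 0.4) and smoking 25 points (0.5 SD) | 0.20 + 0.125 = 0.325 | 16.5% |

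**4. The same situation with adjustment (simulation).** With age 0.5 SD and correlation 0.5, the unadjusted test rejects in 12.0% of runs and a model with group and age in 5.1%. In the last row of the table the figures are 16.5% and 5.2%. If that imbalance runs the other way and the true effect is 0.8 SD, the t-test sees 0.8 − 0.325 = 0.475 SD. Its power is about 30%, against about 72% with adjustment.

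**5. Where the excess arises.** In the simulation with age 0.5 SD and correlation 0.5, the age check was non-significant in 66.1% of runs. In those runs the unadjusted outcome test rejected in 6.3%. In the other 33.9% the rate is (0.1205 − 0.6614 × 0.0634) / 0.3387 = 23%. So most of the excess false positives fall where the check does flag a difference, which is where section 10.2 prescribes nothing.

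**6. Cost of adjusting.** With balanced groups and SD 1 the unadjusted SE is √(2/20) = 0.316. With three covariates of which only age is prognostic (slope 0.5), it falls to 0.284. If none is prognostic, power at 0.8 SD drops from about 70% to about 66%.

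**The case against.** - **The protocol has an argument for comparability.** It draws patients from a period when both treatments were in use and says age and co-morbidity did not steer selection. That is a reasonable design argument. But it mentions neither sex nor smoking, and it concerns the time of treatment. Those analysed are later survivors without disease (section 6.1) who return a consent form (section 8.2) and can undergo MRI (section 6.3).
- **A reader might infer that the group difference is confounded.** The documents do not show this. No imbalance or direction is reported, and the bias is conditional on one. With small imbalances and weak effects the type I error is 5.7%, close to nominal.
- **A reader might infer that every planned result is affected.** That is too broad. Objectives 4 and 5 compare current with baseline CAC and ECG, which would partly offset pre-existing differences, although section 10 describes no such analysis. Objectives 6 and 7 relate findings to radiation dose and are not group comparisons.
- **An SAP may add adjusted analyses.** It may, and section 10.1 does not forbid them. But the protocol itself names the comparison, and it is unadjusted.
- **It is an exploratory pilot.** This stands and lowers the priority. It does not remove the point, because estimating the group difference is a stated aim.
- **Adjustment is not free or complete.** This also stands. Section 4 does not say to which time smoking status refers. A linear model does not suit yes/no endpoints such as valve disorders. Three covariates cannot remove unmeasured differences.

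**Conclusion.** The point holds in conditional form. The stated method has no protection against imbalance in factors that the protocol itself calls causes of the outcome, and the risk-factor test is too weak to show balance (34% power at 0.5 SD). If there is an imbalance, a plausible range is a bias of about 0.1 to 0.4 SD and a type I error of about 6 to 25%. That range rests on assumed imbalances, assumed covariate effects and a two-sided 5% level, none of which the protocol gives. The direction of the argument does not depend on them, but the size does. Bonferroni does not help, since it addresses multiplicity and not bias. It should be fixed before analysis. The documents do not support calling it a critical flaw, because no imbalance is shown and the study is an exploratory pilot.

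**What to change.** **Section 10.1, continuous parameters.** Make the main comparison a linear model with group, age, sex and smoking history (as recorded, preferably up to treatment). Report the adjusted difference with its 95% CI and keep the t-test as supportive.

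**Section 10.1, yes/no endpoints.** Use an analogous adjusted model where event numbers allow. Otherwise report the unadjusted difference and label it as such.

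**Section 10.2.** Show risk factors, including sex, by group with standardised differences, and do not use p-values to judge balance.

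**Cost.** A few lines of text, three degrees of freedom, and a slight loss of power if no covariate is prognostic (about 70% to 66% at 0.8 SD). No extra patients are needed. The covariates are already listed in section 4, though the timing of smoking status needs to be stated. Frequency-matching on sex and age band at invitation is an option if enough survivors respond, but it is not part of the required change.

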### **10.2. Other study parameters**

Risk factors for cardiac and pulmonary complaints will be presented in frequency tables and tested for statistical significant differences between both groups using an independent t-test

Location of focal wall abnormalities and arteriosclerosis and its relation to high dose regions will be presented in a table.

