## **2. OBJECTIVES**

Primary Objectives:

The main objective of this study is to determine the most suitable diagnostic test to identify cardiopulmonary (dys)function in EC survivors treated with neo-CRT followed by surgical resection. Furthermore, we want to estimate the difference in cardiopulmonary (dys)function in EC survivors treated with neo-CRT followed by surgical resection compared to EC survivors who were treated with surgical resection alone.

1. To determine the differences in clinical cardiac and pulmonary events, (cardiac ischaemia, heart failure, arrhythmia, valve disorders, pulmonary hypertension, COPD) as clinically diagnosed since treatment between patients treated with neo-CRT and surgery alone.
2. To determine the difference in other (subclinical) parameters as tested by echo cardiogram, 6 minute walking test, CT scan, MRI scan and biomarkers.
3. To analyse the current CAC scores in both patient groups.
4. To determine the difference between the baseline and current CAC scores.

5. To determine the difference between ECG findings currently and on baseline.
6. To correlate the different subclinical imaging parameters to the radiation dose given to the heart and lungs
7. To correlate CAC scores with the given dose distribution on plannings CT scan

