#### *6 minute walking test:*

Gives an estimate of the general functioning status of the patients during follow up. It is known to correlate with maximum oxygen uptake and physical fitness without laboratory test [24].

*Laboratory tests:*

NT pro BNP and hs TNT are known markers in cardiology for myocardial damage and “volume overload” like in diastolic dysfunction. Blood markers like cholesterol, CRP, HbA1 will help determining the baseline risk on cardiac events. eGFR will be checked before gadolinium is infused in order to minimize risks on its possible side effects. It is necessary to determine hematocrit for calculation of the extracellular volume (ECV).

*ECG*

Simple screening instrument to indicate hypoxia, pericarditis, past infarctions, bundle branch blocks and rhythm disorders

*Echocardiogram:*

An echocardiogram is performed as a safe non-invasive screening technique, which is able to measure hypertrophy of the myocardium, pericarditis, wall motion disorders, blood flows and pressures, which are functional parameters who could indicate pulmonary hypertension and diastolic- or systolic dysfunction and valve disorders[25].

The echocardiographic assessment will be performed by the Echocardiography Core lab ([www.G-ICL.com](http://www.G-ICL.com)) facility, of the UMCG. The echocardiographic protocol includes assessments of systolic and diastolic function of both ventricles according to the guidelines of the European Association of Cardiovascular Imaging (EACVI). Specifically we will assess:

1. Tricuspid annular plane systolic excursion (Tapse)
2. Velocity of the tricuspid annular systolic motion (RV s')
3. Right ventricle fractional area change
4. Doppler notching of right ventricular outflow tract signal
5. Tricuspid valve Doppler velocity
6. Pulmonary valve Doppler velocity
7. Myocardial performance index (Tei index)
8. Pulmonary artery acceleration time
9. Pulmonary valve end diastolic velocity
10. Cardiac Output
11. Left ventricle systolic function

- 12.Left ventricle diastolic dysfunction
- 13.Valvar abnormalities
- 14.Left ventricle eccentricity index
- 15.Right ventricle strain
- 16.Right atrium volume
- 17.Inferior Caval Vein collapsibility

Also 2D strain echocardiography will be performed to establish subtle changes in myocardial function.

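### Section 10.2 applies a t-test to risk factors tabulated as frequencies, and section 10.1 fixes mean, SD and t-test for every parameter, which suits skewed biomarkers badly

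*Protocol*

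**What the plan says.** Only the protocol is available; a statistical analysis plan may exist but is not shown.

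- **Section 10.2** covers the risk factors for heart and lung complaints and states that these are to be "presented in frequency tables and tested for statistical significant differences between both groups using an independent t-test".
- **Section 4** lists nine cardiac risk factors. Among them are "Smoking status", "Family history on cardiac events", hypertension, diabetes and medication use, all categorical by name. Age is the clear continuous item.
- **Section 10.1** covers the cardiopulmonary parameters and states that they "will be presented by means and standard deviations and will be compared between the groups using an independent t-test, with Bonferroni correction if applicable". The qualifier at the end belongs to Bonferroni, not to the choice of summary or test.
- **Section 2** asks in objective 2 for the difference between groups in "other (subclinical) parameters as tested by echo cardiogram, 6 minute walking test, CT scan, MRI scan and biomarkers". Objective 3 reads "To analyse the current CAC scores in both patient groups".
- **Section 8.2, laboratory tests**, states "NT pro BNP and hs TNT are known markers in cardiology for myocardial damage" and volume overload.
- **Section 1, patient population**, says of the two treatment groups that "we did not select patients on cardiopulmonary co-morbidities or age, so we expect comparable groups". Section 8.1 marks randomisation as not applicable, and section 7 sets 20 patients per group.

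**The concern.** The display and the test in section 10.2 do not belong together. A t-test needs a number for each patient. An unordered factor with several levels has no natural numbers, so the p-value reflects how the levels were coded. This matters because the groups are not randomised and the protocol only expects them to be alike. The section 10.2 comparison is the only stated between-group test of those factors.

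Section 10.1 raises a related problem. The pilot is meant to identify which diagnostic tests deserve a later cohort study. A rule that works for roughly normal imaging measures but loses power on skewed blood markers tilts that choice against the markers. Mean and SD would also describe such markers poorly.

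**Working it through.** The protocol gives no alpha, effect size, SD or distribution, so there is no figure of its own to reproduce. From the documents come 20 patients per group, the named tests and the list of parameters. Two-sided alpha 0.05 and all distribution shapes below are assumptions.

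**1. Three-level factor.** Invented table: 4/12/4 in one group, 8/4/8 in the other.

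- Codes 0/1/2: the means are (12 + 8)/20 = 1.0 and (4 + 16)/20 = 1.0. The difference is 0, so p = 1.00.
- Codes 1/0/2: the means are (4 + 8)/20 = 0.6 and (8 + 16)/20 = 1.2. The sample variances are (1.0 − 0.36) × 20/19 = 0.674 and (2.0 − 1.44) × 20/19 = 0.589, pooled 0.632. Then t = 0.6/√(0.632 × 2/20) = 2.39 on 38 df, p = 0.022.
- Chi-square: the expected counts are 6/8/6 in each group. The statistic is 4 × (2²/6) + 2 × (4²/8) = 6.67 on 2 df, p = 0.036.

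Simulated power (40,000 runs):

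| Level probabilities | t, codes 0/1/2 | t, codes 1/0/2 | t, codes 0/2/1 | Chi-square |
|---|---|---|---|---|
| .20/.60/.20 v .40/.20/.40 | 5% | 66% | 65% | 66% |
| .40/.40/.20 v .20/.40/.40 | 38% | 12% | 12% | 29% |
| .50/.35/.15 v .20/.40/.40 | 62% | 12% | 26% | 50% |
| No difference (thirds) | 5% | 5% | 5% | 5% |

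Rows 2 and 3 show that natural scores beat chi-square when an ordered factor shifts one way.

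**2. Yes/no factor.** On 0/1 data with N = 40, chi-square = N·t²/(t² + 38). The t-test critical value is 2.024, so it rejects when chi-square exceeds 40 × 4.098/42.098 = 3.89, against the usual 3.84. Enumeration of all 20 v 20 tables finds none where the two decisions differ, among tables where both tests exist. The largest type I error of the t-test is 5.3%.

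**3. Skewed biomarker.** Lognormal, 20,000 runs:

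| Log-SD, true ratio | Raw t-test | Wilcoxon | Log-scale t-test |
|---|---|---|---|
| 0.6, 1.75-fold | 75% | 80% | 82% |
| 0.8, 2-fold | 64% | 74% | 76% |
| 1.0, 2.72-fold | 69% | 85% | 87% |
| 1.2, 2.72-fold | 47% | 70% | 73% |

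The loss against Wilcoxon runs from 79.8 − 75.0 = 4.8 points to 69.9 − 47.0 = 22.9 points. With no true difference the raw t-test rejects in 3.4% to 4.8% of runs. For normal data with a standardised difference of 0.9 the order reverses: t-test 79%, Wilcoxon 77%.

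A separate simulation with a fixed shift of 0.8 log-SD agrees. For log-SD 0.5 to 1.5, raw t-test power falls from 64% to 34%, while Wilcoxon stays near 67%.

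As a summary at log-SD 1.0: mean/median = exp(0.5) = 1.65; share of patients below the mean = Φ(0.5) = 69%; SD/mean = √(e − 1) = 1.31, so mean minus one SD is negative.

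Bonferroni would lower power further, but section 10.1 names no family. For illustration, two markers (alpha 0.025) at log-SD 1.0 give 54% v 76%.

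**4. CAC score.** Lognormal with a share of zeros, 3-fold difference, 6,000 runs:

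| Zeros, surgery / neo-CRT | Log-SD | t-test | Wilcoxon |
|---|---|---|---|
| 25% / 10% | 1.6 | 28% | 61% |
| 25% / 25% | 1.6 | 16% | 21% |
| 40% / 40% | 1.6 | 11% | 11% |
| 25% / 25% | 1.2 | 34% | 31% |

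The gain is large in one shape only.

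**The case against.** **The categorical fault is narrow.** Family history, hypertension and diabetes are naturally yes/no, where the t-test and chi-square agree. The protocol does not say how smoking or medication use is coded, and an ordered smoking variable with natural scores can do better than chi-square. The 4/12/4 v 8/4/8 table was chosen so that one coding hides the difference, and the printed frequency table would still show the pattern. All of this stands, and it limits the practical harm. It does not make a comparison of means a valid test for an unordered factor.

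**Distribution checks and fallbacks are usually left to the analysis plan.** That is so, and their absence is not the point here. The protocol has already named the summary and the test. The text does not say raw scale, so a log-scale t-test could be squared with it, but fixing mean and SD points the other way.

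**The size rests on assumed skewness and large shifts.** This is correct. At the low end the loss is 5 points, and for a normal marker the t-test is slightly better.

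**Median and Wilcoxon give no effect estimate, although the protocol wants to estimate a difference.** This has force. For strictly positive markers the log-scale t-test gives a ratio with an interval and had the highest power in the lognormal runs.

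**This is an exploratory pilot with no excess of false positives.** That is true, and it limits the seriousness of the point.

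**Conclusion.** The concern holds. Section 10.2 is wrong as written for any unordered factor with more than two levels, since the answer can move from p = 1.00 to p = 0.022 on coding alone. For yes/no factors the mismatch is one of form.

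In section 10.1 the stated rule is a poor default for skewed markers, with an assumed loss of about 5 to 23 points of power at 20 per group and a misleading summary. For CAC the case is mainly for a better summary, because the power gain may be nil. If section 10.1 is also meant to cover clinical events and present/absent findings, mean and SD describe those poorly too, but the gain there is in presentation.

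The consequence is lost information and not a false claim of effect. It should be fixed.

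**What to change.** **Section 10.2.** Present categorical risk factors as n (%). Test them by chi-square, or by an exact test when cells are sparse, with a trend test for factors that have a natural order. Keep the t-test for continuous items such as age.

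**Section 10.1.** Keep mean (SD) and the t-test for approximately normal echocardiographic, MRI and walking-test measures. Use median (IQR) and the Wilcoxon rank-sum test for skewed biomarkers and CAC. For strictly positive markers a log-scale t-test is an alternative, and its ratio with 95% CI serves the aim of estimating a difference; it does not suit CAC scores that include zeros. Report yes/no findings and clinical events as n (%) with a risk difference and 95% CI.

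**Cost.** Rewording of section 10 only, with no extra data or patients. Three downsides should be accepted knowingly:

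- Wilcoxon gives up about 2 points of power if a marker is in fact normal.
- Chi-square gives up about 9 to 12 points against a scored test for an ordered factor that shifts one way, hence the trend test.
- Fisher's exact test gives up power against chi-square, for example 41% v 53% for proportions of 0.2 v 0.5, so it should be kept for sparse tables.
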